1. STUDY PRODUCT

The study product cerebrolysin is expected to be administered as a single daily dose of 30 mL diluted in 0.9 % sodium chloride up to 100 mL in a 20-min intravenous infusion.

Study group 1: cerebrolysin 30 mL

Study group 2: no cerebrolysin

2 CO-MEDICATIONS

All previously used and concomitant medications must be recorded in the CRF, including the start date and the date of discontinuation, if possible, the maximum total daily dose and route of administration. Then the reason (diagnosis) on the basis of which this special concomitant therapy was prescribed should be specified. Finally, if a concomitant drug is used in preventive regimen, this should be reported on the appropriate CRF page.

3 Acceptable co-medication

Appropriate concomitant medications may be prescribed if the investigator believes there is clinical need:

- Baseline stroke therapy within the general management of the patient can be used without restriction if necessary. At each visit, it is envisaged to register co-medications received by the patient (including dosage and frequency).
- Medications to compensate for abnormality in water and acid-base balance.
- Medications required for adequate treatment of secondary symptoms, including, but not limited to, antihypertensive agents, cardiovascular therapy, antidiabetic agents, if necessary, drugs to normalise sleep disorders (excluding benzodiazepines), antibiotics, and antipyretics.

4. Prohibited co-medications

The use of the following drugs in a clinical study is limited and every effort should be made to avoid taking the following:

- Concomitant use of other neuroprotective or nootropic drugs (e.g., citicoline, memantine, amantadine, erythropoietin, diazepam, investigational neuroprotective drugs; piracetam, pramiracetam, pyritinol, meclosulfonate, glycine)
- Concomitant use of drugs with a vasodilatory effect, such as naftidrofuryl, cinnarizine, flunarizine, nimodipine, nicergoline, pentoxifylline, dihydroergotoxin (codergocrine), vinpocetine, vincamine, or ginkgo biloba
- Antioxidant drugs (e.g., but not limited to lipoic acid, ethylmethylhydroxypyridine succinate)
- Levodopa and dopamine agonists
- Statins within the first 7 days from the disease onset.

5. Previous medications

If necessary, constant dosage of previously used medications can be taken throughout the clinical study.

Any changes to previously used medications should be recorded in the CRF.

6. Drug interactions

To date, no drug interactions for the study product have been reported.

REHABILITATION PROGRAM

Rehabilitation program will be in accordance with ischemic stroke standard of care starting no later than 48 hours post stroke.

EFFICACY EVALUATION

1. DESCRIPTION OF EFFICACY CRITERIA

1. Development of hemorrhagic transformations

Development of hemorrhagic transformations (HT) in ischemic area should be determined based on the results of follow-up brain CT. According ECASS 3 criteria, HT is defined as symptomatic (SHT) when neurological symptom exacerbation according to NIHSS is \geq 4 NIHSS or results in death.

2. NIHSS scale

Neurological deficit is assessed using NIH scale. It is a 15-item scale evaluating level of consciousness, gaze, visual field, facial palsy, motor functions, limb ataxia, aphasia, dysarthria as well as extinction, and inattention (Brott et al, 1989).

Each item has a 3-5 score from 0 to 4, with the highest score being consistent with the most severe disability. The worst score is assigned in case of death.

Drastic improvement - cases of improvement with reduced NIHSS score ≥ 4 one day after the disease debut is considered as "drastic improvement".

3. Modified Rankin Scale

Modified Rankin Scale (Van Swieten et al, 1988) is the scale evaluating general functional outcome. It is used to grade the stroke outcome and post-stroke disability. Modified Rankin scale is the ordinal 7-point scale scoring from 0 (lack of residual symptoms) to 6 (worst) which corresponds to patient death.

4. Neuroimaging techniques

Brain non-contrast CT will be performed at admission, in 24 h, on day 7 and 14 after IVT using standard technique; helical scanning is preferred; minimum section width (post reconstruction) is 5 mm; scanning area - the whole brain; the sections are made without gantry slope.

The sections obtained at admission will be assessed using ASPECTS scale indicating the presence of the symptom of hyperdense middle cerebral artery (MCA) sign.

Hyperdense MCA sing is determined based on the density of affected and normal vessels. Absolute density of affected MCA > 43 Hounsfield units and affected/normal MCA > 1.2 on non-contrast CT is considered as a positive symptom.

24 hours, on day 7 and 14 after IVT non-contrast CT is performed to evaluate presence of haemorrhagic transformation.

Advance brain imaging protocol:

Non-contrast MRI will be performed at admission. Axial DWI, FLAIR, MR-angiography are performed using standard techniques.

In 24 h after IVT non-contrast brain MRI is carried out in DWI, DTI and MR-angiography.

DWI is used to determine infarction volume using ABC/2 formula.

Axial DTI is performed using standard technique. The section with the largest changes will be selected from the whole DTI scan collection at postprocessing step. Region of interest (ROI) should include the whole infarction area at this section, the reference area being the contralateral hemisphere mirror image. The protocol will specify the number of the section selected, mean

values of fractional anisotropy (FA), mean diffusivity (MD), axial diffusivity (AD), radial diffusivity (RD) both in ROI and in reference area.

On day 14 non-contrast brain MRI will be performed in DTI.

DTI will be made and processed in axial methods using the technique described above. Quantitative parameters are evaluated at the level of the pre-selected section (see DTI scans 24 h after IVT).

Also on day 14, CT-perfusion will be performed.

The patients head should be fixed using a restrainer to reduce motor artefacts; 40 mL of contrast (Omnipaque, 300 mg/mL of iodine) should be administered as a bolus injection into median cubital vein using an injector at 5 mL/s rate, further 40 mL of 0.9 % sodium chloride was administered at the same rate. The scanning will begin in 5 seconds; 80 kV, 100 mA; time resolution - 1 scan every 2 second for the first 60 seconds, then 1 scan every 30 seconds during the next 3 min. Overall scanning time is 4 min. At such scanning mode radiation dose should not exceed 3.2-3.5 mSv (J. Hom at al., 2011). The sections will be made without gantry slope.

Post-processing will be made at GE Workstation. The scan with the largest changes will be chosen out of the scans obtained. The first phase will be processed using deconvolution algorithms insensitive to delay. Region of interest (ROI) is the whole hypodense area, reference area is the contralateral hemisphere (mirror image). The BBB permeability maps (PS) will be processed using Johnson and Wilson kinetic model. The pre-selected section will be used. The protocol will specify PS values (permeability-surface area product) both in ROI and in reference area.

In addition to standard contraindications to non-contrast CT, CT-perfusion and MRI, no additional contraindications are in place in this study.

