The minimum detectable odds ratio (OR) for any hemorrhagic transformation (HT) was assumed as low as 0.5. The probability of any HT among controls was expected as high as 0.2. The significance level, power, and correlation of any HT between the arms were set at the values recommended by the software manual, which were 0.05, 0.8, and 0.3, respectively. As it was a pilot study, any HT was chosen for the calculation because it encompassed all types of HT. The drop-out rate is expected as low as 0.1. A 1:2 design was chosen to reduce the sample size by approximately 30%.

Thus, the expected sample size is 264: 88 patients in the Cerebrolysin group and 176 subjects in the control arms.

Inclusion Criteria:

- Confirmed diagnosis of acute ischemic stroke
- Age ≥ 18 years
- Onset of stroke symptoms within 4.5 h before initiation of rtPA administration

Exclusion Criteria:

- Current or previous intracranial hemorrhage
- Symptoms suggestive of subarachnoid hemorrhage, even if CT scan was normal
- Imaging data on admission suggestive of a brain tumor, arteriovenous malformation, brain abscess or intracerebral aneurism
- Previous history of brain tumor, intracranial aneurism or arteriovenous malformation
- Previous history of brain or spine surgery
- Acute myocardial infarction within the previous 3 months
- Major bleeding, current or within the previous 6 months
- Gastrointestinal or genitourinary bleeding within the previous 3 months
- Confirmed relapse of gastric or duodenal ulcer
- Unknown time of symptom onset
- Minor (NIHSS score <4) or severe stroke (NIHSS score >25) on admission
- Seizure at stroke onset
- Stroke or serious head trauma within the previous 3 months
- Administration of heparin within the 48 h preceding the stroke onset, with an activated partial thromboplastin time at presentation exceeding the upper limit of the normal range
- Platelet count $<100 \times 10^{9}/L$
- Systolic blood pressure >185 mm Hg or diastolic blood pressure >110 mm Hg
- Blood glucose <50 mg/dL (2.8 mmol/L) or >400 mg/dL (22.2 mmol/L)
- Oral anticoagulant treatment
- Major surgery or severe trauma within the previous 3 months
- Other major disorders associated with an increased risk of bleeding (neoplasm, bleeding diathesis, acute pancreatitis, infective endocarditis, pericarditis, severe liver and kidney failure)
- Known allergic reactions to rtPA, Cerebrolysin and its components
- Pregnancy and lactation
- Endovascular treatment

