Additional Inclusion Criteria for Advanced Brain Imaging:

- No contraindications to magnetic resonance imaging (MRI) and computed tomography (CT) perfusion (CTP) study
- Stroke in the middle cerebral artery territory with a minimum diffusion-weighted imaging (DWI) lesion diameter of 20 mm on admission

Study product, dose and method of administration:

Both groups would receive a standard dose of 0.9 mg/kg recombinant tissue plasminogen activator (rtPA; alteplase) administered by IV infusion within 4.5 h after symptom onset. In addition, measures of standard care for stroke patients would be applied for both groups. Patients in the Cerebrolysin group would additionally receive 30 mL of Cerebrolysin diluted in 100 mL of normal saline administered intravenously through a separate IV line over 20 min. No treatment with other neuroprotective agents would be allowed.

Length of the Study:

Cerebrolysin treatment would be initiated simultaneously with IVT and continued once daily for 14 consecutive days. A follow-up period would be 90 days for each patient. The visits would be scheduled as follows: screening (on admission), in 24 h (visit 1), on day 7, 14, and 90 (visit 2, 3, and 4, respectively).

Endpoint evaluation:

Primary endpoint evaluation:

The study primary endpoints would be any and symptomatic HT verified on a follow-up CT scan. Symptomatic HT would be defined according to the ECASS III trial: any apparently extravascular blood in the brain or within the cranium that is associated with clinical deterioration, as defined by an increase of 4 points or more in the score on the NIHSS, or that lead to death and that is identified as the predominant cause of the neurologic deterioration.

Secondary endpoint evaluation:

Secondary endpoints would be the functional outcome measured with the National Institutes of Health Stroke Scale (NIHSS) and modified Rankin scale (mRS) as well as drug safety.

Favorable functional outcome would be defined as the mRS score of ≤ 2 at V4 (day 90).

The NIHSS score at V3 (day 14) would be considered as a marker of short-term neurological recovery.

Patients in both arms would be monitored for any adverse events (AE) at V1-3, including changes in vital signs, general and neurological condition, electrocardiogram, and routine laboratory tests (liver and kidney function tests, complete blood count).

Additional evaluation (advanced brain imaging):

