6. REFERENCE INFORMATION

Stroke is a severe disease and one of the leading causes of disability and lethality globally. Ischemic stroke (IS) accounts for the most part of stroke cases overall, i.e. up to 85 %. Reperfusion therapy is currently one of the verified effective IS treatment. IV TLT is deemed to be effective in improving neurological symptoms while reducing NIHSS by ≥ 4 within one day. One of the factors of reperfusion therapy failure may be reperfusion damage developing after recanalisation of a cerebral vessel and generally is considered as a consequence and progression of abnormal ischemic effects. Therefore, recanalisation of a clotted or embolised cerebral vessel within "therapeutic window" promotes preservation of the most part of inactive though viable neurons; meanwhile recovery of blood flow in ischemic area may cause reperfusion-induced cerebral tissue damage of various grades, thus aggravating peracute IS.

One of manifestations of reperfusion damage is BBB failure with increased permeability or impaired integrity resulting in exacerbation of edema of ischemic area or in hemorrhagic transformation (HT) of the ischemic area. Meanwhile, HTs are also reported without recanalisation effect and outside of the ischemia area; this is due to both cerebral tissue damage in hypoperfusion area and due to toxic effect of the thrombolytic agent. Thus, TLT increases the risk of HT 4-10-fold by activating matrix metalloproteinase 9, 2, 3 in neutrophils, endothelium, astrocytes, and platelet-derived growth factor-CC, however the pathogenesis of early (up to 24 hours) HTs and late HTs varies. While early HTs are associated with acute processes of BBB damage, the late ones are due to cerebral tissue inflammation and vascular remodelling. Clinically, the most relevant are symptomatic HTs (SHT) associated with aggravated neurological symptoms \geq 4 according to NIHSS scale or lethality (according to ECASS III 2008, 2016). Generally, SHTs have the nature of parenchymatous haematomas (hemorrhages, PH2 according to neuroimaging HT classification) exceeding 30 % at ischemic area. Smaller haematomas and petechia-like HTs are asymptomatic (HI-1, HI-2, PH-1).

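### The CT rule for any HT makes 5 mm a minimum section width, so it permits thicker sections without limit and does not require one width across centres and visits

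*Protocol*

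**What the plan says.** The Neuroimaging techniques item of the protocol's Description of Efficacy Criteria sets the rules for the non-contrast brain CT done at admission, 24 hours, day 7 and day 14. It calls for standard technique, states that "helical scanning is preferred", and adds that "minimum section width (post reconstruction) is 5 mm". No upper limit and no single fixed width for non-contrast CT appears anywhere else in the protocol.

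The follow-up scans carry the primary endpoint. The synopsis states: "The study primary endpoints would be any and symptomatic HT verified on a follow-up CT scan". Its sample size paragraph explains that "any HT was chosen for the calculation because it encompassed all types of HT". The Reference Information section lists the small forms as HI-1, HI-2 and PH-1 and treats them as asymptomatic. It describes symptomatic HT as generally a large parenchymal haematoma (PH2).

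Eight centres recruit. Under Measures to Minimise/Prevent Systemic Bias, scans are read locally by radiologists blinded to treatment, and one simple randomisation list serves all centres.

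The additional imaging is specified more tightly. The synopsis gives a slice thickness of 4.5 mm with a 1 mm gap for DTI, and 5 mm for CT perfusion.

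**The concern.** A minimum on section width points the wrong way for a detection endpoint. A site that reconstructs at 2.5 mm breaks the rule as written, and a site that uses 8 or 10 mm complies. Thicker sections average a small bleed with the tissue around it and lower its contrast. Small bleeds belong to any HT by design, so the rule leaves open the sensitivity of one of the two primary endpoints.

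Nothing ties the width to one value across centres, or across the three follow-up scans of one patient. If widths differed, part of the variation in any HT would come from the reconstruction setting. Sites could also read the word in opposite ways, some as a ceiling and some as a floor, and each believe that it complies.

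What is at stake is the number of detected events, and so the power of the any-HT comparison. The day-14 infarct volume, which is also measured on CT (ABC/2), would gain from a fixed width too.

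**Working it through.** The protocol gives no figure to reproduce here. The first step is to read the rule; the rest illustrates its possible consequence.

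**1. What the rule allows.** A minimum of 5 mm means width ≥ 5 mm. So 2.5 mm is excluded, and 5, 8 and 10 mm are all allowed. The documents do not state the widths in use at the centres; 8 and 10 mm are examples of what the text permits.

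**2. Contrast of a small bleed.** Assumptions, none from the protocol: a bleed 3 mm thick, density 60 HU, surrounding tissue 25 HU (range 25 to 35), linear partial-volume averaging.

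Contrast = (bleed − tissue) × min(1, thickness / width)

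| Width | Tissue 25 HU | Tissue 30 HU | Tissue 35 HU |
|---|---|---|---|
| 2.5 mm | 35 × 1 = 35 | 30 | 25 |
| 5 mm | 35 × 0.6 = 21 | 18 | 15 |
| 8 mm | 35 × 0.375 = 13.1 | 11.3 | 9.4 |
| 10 mm | 35 × 0.3 = 10.5 | 9 | 7.5 |

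**3. Allowing for noise.** Thicker sections are less noisy. Assume that noise is proportional to 1/√width. Contrast-to-noise relative to 5 mm (tissue 25 HU) is then:

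- 2.5 mm: (35/21) × √(2.5/5) = 1.18
- 8 mm: (13.125/21) × √(8/5) = 0.79
- 10 mm: (10.5/21) × √(10/5) = 0.71

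For any bleed no thicker than 5 mm, the 8 and 10 mm ratios reduce to √(5/width). They therefore do not depend on the assumed densities. A thicker bleed loses less, and one at least as thick as the section loses nothing in this model.

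**4. Effect on the comparison if events are missed.** From the protocol's sample size paragraph: control rate 0.20, odds ratio 0.5, 88 and 176 patients. The Cerebrolysin rate is 0.2 × 0.5 / (1 − 0.2 + 0.2 × 0.5) = 0.111. Assume that detection falls equally in both arms. The arms are treated as independent, with two-sided α 0.05:

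Power = Φ[(d − 1.96 × SE₀) / SE₁], where d is the difference in rates, SE₀ the pooled and SE₁ the unpooled standard error.

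- Full detection: d = 0.0889, SE₀ = 0.0491, SE₁ = 0.0451, power = 0.44
- 90% detection: power = 0.39
- 80% detection: d = 0.0711, SE₀ = 0.0448, SE₁ = 0.0410, power = 0.34
- 70% detection: power = 0.30

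The starting value of 0.44 is not the protocol's 0.8, which comes from a matched case-control calculation. Only the fall from one line to the next is used here. The detection rates are assumptions and are not derived from step 3.

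**5. Effect on the odds ratio.** At 80% detection, 0.20 and 0.111 become 0.16 and 0.089. The odds ratio is (0.0889/0.9111) / (0.16/0.84) = 0.0976/0.1905 = 0.51, against 0.50 with full detection.

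**The case against.** The strongest reply is that this is a wording query and no more. The same item calls for standard technique, the only other CT width in the protocol is also 5 mm, and 'minimum' may be a translation slip or may mean a minimum technical standard. No passage gives a site's width or says that sites differ. Readers are blinded and one list serves all centres, so any loss should be similar in both arms, and the odds ratio hardly moves (0.50 to 0.51 at 80% detection). Three follow-up scans give repeated chances to see a bleed. The protocol declares its analysis exploratory. Once noise is counted, the gain from 2.5 mm over 5 mm is small (1.18 against 1.00).

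Most of this stands, and it limits the point. It does not remove it: as written, the rule still permits widths at which contrast-to-noise falls to 0.79 or 0.71 of the 5 mm value, and nothing elsewhere closes that gap.

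A reader might infer three stronger things that the documents do not support:

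- **That small bleeds are in fact missed differently by site.** The text permits this and does not show it.
- **That a hyperdense-artery covariate is misclassified by site.** The absolute-density rule, "Absolute density of affected MCA > 43 Hounsfield units and affected/normal MCA > 1.2 on non-contrast CT is considered as a positive symptom", is applied to admission scans ("The sections obtained at admission will be assessed using ASPECTS scale indicating the presence of the symptom of hyperdense middle cerebral artery (MCA) sign") and not to the scans that decide HT. It also has a ratio condition. The Statistical Methods section names univariate and multivariate regression but does not list this sign, or any other, as a covariate.
- **That this sign should be read on the thinnest reconstruction available.** That width would itself vary by scanner, and the protocol does not say for which width the 43 HU cut-off was set.

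**Conclusion.** The point holds in a narrow form and is minor. The protocol's width rule for the scans that determine any HT is a lower bound with no ceiling, and it does not require the same width across centres or visits. That much is read directly from the text.

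The consequence is possible, not demonstrated: lower sensitivity to HI-1, HI-2 and PH-1, and noise between sites. On the assumed values, contrast falls from 21 HU at 5 mm to 11 to 13 HU at 8 to 10 mm, or to about 0.7 to 0.8 of the 5 mm contrast-to-noise. If this led to missed events at equal rates in both arms, the any-HT comparison would lose some power: about 0.10 at an assumed 80% detection (0.44 to 0.34).

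No bias towards one arm is expected. Symptomatic HT, generally a large haematoma, would be little affected. All densities, thicknesses, widths other than 5 mm and detection rates are assumptions.

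**What to change.** In the Neuroimaging techniques item, replace the minimum with a maximum of 5 mm after reconstruction, or name 5 mm as the single required width. Add one sentence: the same reconstruction width is used at all centres and at all visits of a patient.

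The cost is one word and one sentence. Where a site would have used thicker sections, its images will be slightly noisier. Because helical scanning is preferred but not required, a site that scans sequentially would have to set the width at acquisition, since thinner reconstructions cannot be presumed available afterwards.

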2. EFFICACY CRITERIA

NIHSS scoring should be made at screening, at baseline visit before the first administration of the study product, within 24 hours, according to the protocol of thrombolytic therapy, in 24 hours (visit 1), on day 7 (visit 2), on day 14 (visit 3).

Modified Rankin Scale scoring will be made at the baseline visit before the first administration of the study product on day 14 (visit 3) and on day 90 (visit 4).

Brain imaging findings will be reported by radiologists.

Evaluation of efficacy criteria will be analysed in accordance with the provisions of the statistical analysis plan.

SAFETY EVALUATION

1. SAFETY DATA

Safety data should include AEs, vital signs and laboratory tests including haematology, serum chemistry, and urinalysis.

All the AEs developing after signing informed consent should be recorded regardless of whether they are considered as related or unrelated to the study product. At each visit, the investigator should detect AEs and evaluate them. AEs should be monitored until reduction of intensity, classification as medically stable or until loss to follow-up.

AEs should be recorded directly in CRF. Analysis will be performed in accordance with statistical analysis plan.

The data will be summarised and analyzed using tables and diagrams for demographic/baseline characteristics and observations and efficacy/safety evaluations. Standard parameters of descriptive summary statistics (e.g. calculation of arithmetic mean, standard deviation, median, minimum/maximum - quartiles if applicable) will be calculated for continuous variables. Categorical data will be presented in frequency tables showing numbers and proportions. Tabulated summaries will be presented for each treatment group and in general for all patients. For individual parameters, lists of data for specific patients sorted by treatment group, center, patient number and visit will be complied. For OR calculation logistic regression analysis will be used (both univariate and multivariate) using Firth method due to relatively small sample size and rare nature of haemorrhagic events. Missing data will be analysed for patterns and where possible will be processed using multiple imputation.

ETHICAL PRINCIPLES

INDEPENDENT ETHICS COMMITTEE (IEC)/INSTITUTIONAL REVIEW BOARD (IRB)

Recruitment of patients will not be allowed before IEC/IRB written authorisation/positive decision on the study performance is obtained.

No protocol deviations or changes are allowed without written approval/positive decision of IEC/IRB concerning the relevant amendment to the protocol except for the cases when the risk for the patient should be eliminated immediately or when the change(s) deal with logistic or administrative aspect(s) of the study (e.g. change of monitor, phone number, etc.).

ETHICS PRINCIPLES

The clinical study will be carried out in accordance with the protocol, ethics principles outlined in Helsinki Declaration, applicable GCP regulations and requirements of regulatory authorities.

DATA PROCESSING AND RECORD-KEEPING

The data recorded in CRF taken from source documents should be consistent with the source documents while discrepancies should be explained.
